5.2.1.5 Replacement of Subjects in the Dose Evaluation Period

In order to determine safety, all subjects selected must meet the criteria for evaluability in Cycles 1 and 2. Subjects are considered non-evaluable for DLT assessment and will be replaced if:

- They are enrolled but not treated
- They discontinue from the trial prior to completing all the safety evaluations other than treatment-related AEs
- If they receive less than 90% of the total pembrolizumab or dinaciclib in Cycles 1 and 2 (eg, because the infusion had to be discontinued due to an infusion reaction) and did not experience a DLT.

Non-evaluable subjects will not be counted toward the total for Dose Evaluation. If a subject experiences a DLT in Cycles 1 or 2, trial treatment may be discontinued following discussion between the Sponsor and investigator. However, if the subject is deriving clinical benefit from the trial treatment, the subject may be allowed to continue after discussion between the Sponsor and the investigator.

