5.2 Trial Treatment(s)

The treatments to be used in this trial are outlined below in [Table 2](#).

Table 2 Trial Treatments

Drug	Dose/ Potency	Dose Frequency	Route of Administration	Treatment Period	Use
Pembrolizumab (MK-3475)	200 mg	Every 21 days	IV infusion	Until PD, or up to a maximum of 35 cycles (approximately 2 years)	Investigational
Dinaciclib (MK-7965)	14 mg/m ² (Cycle 1 dosing per Table 3)	Table 3	IV infusion	Until PD, or up to a maximum of 35 cycles (approximately 2 years)	Investigational

Abbreviations: IV = intravenous; PD = progressive disease.

Subjects will receive pembrolizumab and dinaciclib as described in [Table 3](#). In Cycle 1, pembrolizumab 200 mg IV (30-minute infusion) will be administered on Day 1; dinaciclib 7 mg/m² IV (2-hour infusion) will be administered on Day 1, and 10 mg/m² IV on Day 8. Each cycle is 21 days. In Cycle 2 and beyond, pembrolizumab will be administered on Day 1, and dinaciclib 14 mg/m² will be administered on Day 1 and Day 8.

Table 3 Dosing Schedule of Pembrolizumab and Dinaciclib

Cycle	Day	Pembrolizumab	Dinaciclib
Cycle 1	1	200 mg	7 mg/m ²
	8	-	10 mg/m ²
	15	-	-
Cycle 2+	1	200 mg	14 mg/m ²
	8	-	14 mg/m ²
	15	-	-

If there are ≥ 5 subjects with DLTs within the initial cohort of 12 subjects in Dose Evaluation, dinaciclib dosing will be evaluated according to Section 5.2.1.3.4 and [Table 13](#).

Trial treatment should begin on the day of treatment allocation or as close as possible to the date on which the subject is allocated/assigned. Treatment allocation by non-random assignment will be done using an IVRS/IWRS.

Dinaciclib and pembrolizumab will be provided centrally by the Sponsor or locally by the trial site, subsidiary or designee, depending on local country operational or regulatory requirements.

The investigator shall take responsibility for and shall take all steps to maintain appropriate records and ensure appropriate supply, storage, handling, distribution and usage of trial treatments in accordance with the protocol and any applicable laws and regulations.

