5.2.1.3.3 Dinaciclib Dose Modifications

Dinaciclib dose modifications for hematologic toxicity will be based on laboratory and clinical assessment performed on Day 1 of each cycle. The dinaciclib dose will not be reduced for cytopenias that have resolved by Day 1 of the next cycle. Dose adjustments or delays due to hematologic toxicity apply to Day 1 of each cycle. There will be no adjustments for Day 8 hematologic results. Dose delays and modifications for dinaciclib due to hematologic toxicity are described in [Table 8](#). Dose delays and modification for dinaciclib for nonhematologic toxicity are described in [Table 9](#). Dose levels to be used for dinaciclib dose modification are described in [Table 10](#). If dinaciclib is held on Day 1, pembrolizumab

should be held as well. If Day 8 toxicity causes dose delay, subject should be retested within visit window in order to identify earliest dosing opportunity. If dose cannot be given within visit window, then Day 8 dose should be skipped.

Table 8 Dinaciclib Dose Modification for Hematologic Toxicity

Criteria for Start of Each Cycle	Action ^a

If ANC $\geq 1.0 \times 10^9/L$ at C1D1 predose, then action^a should be taken if ANC at subsequent Day 1 predose is $< 1.0 \times 10^9/L$
 
If ANC $< 1.0 \times 10^9/L$ at C1D1 predose, then action^a should be taken if ANC at subsequent Day 1 predose is more than 20% lower than C1D1 predose level
	
Delay for up to 3 weeks until recovery. Reduce subsequent doses by 1 dose level. Discontinue subject if already at the lowest dose level or if the subject's ANC has not recovered in 3 weeks.

If platelet count $\geq 50 \times 10^9/L$ at C1D1 predose, then action^a should be taken if platelet count at subsequent Day 1 predose is $< 50 \times 10^9/L$
 
If platelet count $< 50 \times 10^9/L$ at C1D1 predose, then action^a should be taken if platelet count at subsequent Day 1 predose is more than 20% lower than C1D1 predose level
	
Delay for up to 3 weeks until recovery. Reduce subsequent doses by 1 dose level. Discontinue subject if already at the lowest dose level or if the subject's platelet count has not recovered in 3 weeks.

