
^aAction is applied regardless of toxicity causality. If a subject's count recovers within the +/-3 day visit window, then no dose reduction is required. However, if subject's count recovers outside the +/-3 day visit window, then dose reduction guidance outlined above applies. Must hold both pembrolizumab and dinaciclib if a hold is required.
 
Abbreviations: ANC = absolute neutrophil count; C1D1 = Cycle 1 Day 1.
	

For any nonhematologic toxicity that results in dose delay, treatment may be delayed for up to 3 weeks until resolution of toxicity to \leq Grade 1 (Table 9).

Table 9 Dinaciclib Dose Modification for Nonhematologic Toxicity

Criteria	Action
TLS requiring dialysis	Reduce subsequent doses by one dose level. Resume treatment, as an inpatient, only after complete recovery with return to baseline lactate dehydrogenase and electrolytes. If well tolerated, further treatment may continue as an outpatient. If TLS requiring dialysis occurs after dose reduction, the subject must be discontinued.
Post-treatment hyperkalemia with K ⁺ rising above ULN, occurring during dose-escalation in Cycle 1	Manage hyperkalemia per standard of care. Continue with the current dose of dinaciclib and delay dose-escalation until dinaciclib can be administered without a rise in K ⁺ . For example, post-treatment hyperkalemia is noted on C1D1 following 7 mg/m ² dose. C1D8 dose is not escalated and treatment continues at 7 mg/m ² with no hyperkalemia. C2D1 dose is increased to 10 mg/m ² and C2D8 dose is increased to 14 mg/m ² .
Any diarrhea	Diarrhea should be treated with oral loperamide 4 mg followed by loperamide 2 mg after each additional episode of diarrhea to a maximal dose of 16 mg per day, provided there is no clinical evidence of infectious diarrhea.
≥ Grade 3 diarrhea after loperamide	Reduce subsequent doses by one dose level. Discontinue subject who continues to experience ≥ Grade 3 diarrhea despite dose reduction and loperamide. Discontinue subject if already at the lowest dose level.
≥ Grade 3 nausea/vomiting	Add antiemetic agents as appropriate. Reduce subsequent doses by one dose level, only if subject continues to have ≥ Grade 3 toxicity despite maximum antiemetic therapy. Discontinue subject with persistent ≥ Grade 3 nausea/vomiting despite dose reduction and antiemetics. Discontinue subject if already at the lowest dose level.

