5.2.1.3.4 Dinaciclib Dose Evaluation

During Dose Evaluation, the first 12 subjects will receive pembrolizumab 200 mg on Day 1 of each cycle and Dose Level 0 of dinaciclib as described in Table 3 and Table 11.

Table 11 Dinaciclib Dose Levels

Dose Level	Dose of Dinaciclib
Level 0	C1D1: 7 mg/m ² ; C1D8: 10 mg/m ² ; C2D1+: 14 mg/m ²
Level -1	C1D1: 7 mg/m ² ; C1D8: 10 mg/m ² ; C2D1+: 10 mg/m ²
Level -2	C1D1: 7 mg/m ² ; C1D8: 7 mg/m ² ; C2D1+: 7 mg/m ²
C1D1: Cycle 1 Day 1 C1D8: Cycle 1 Day 8 C2D1+: Cycle 2 Day 1 and beyond.	

DLTs observed in Cycle 1 and Cycle 2 will be used to evaluate the dose level. If 4 or fewer subjects at Dose Level 0 have a DLT, the Signal Detection phase of the trial will be opened. Table 12 below summarizes the probabilities of observing the numbers and percentages of subjects under different assumptions of true DLT rate θ_0 , which can be interpreted as the one-sided p-values for testing the null hypothesis that the true DLT rate is less than θ_0 . These criteria are considered non-binding guidelines; recommendations would not be based solely on statistical grounds, as many other factors (ie, all aspects of the data from the trial) may be part of the decision process.

Table 12 Probability of Observing the Number (%) of Subjects with DLT

Observed Number (%) of Subjects	Probabilities (p-values) Under Different Assumptions				
	$\theta_0 = 0.20$	$\theta_0 = 0.25$	$\theta_0 = 0.30$	$\theta_0 = 0.35$	$\theta_0 = 0.40$
2 (16.7%)	0.442	0.609	0.747	0.849	0.917
3 (25.0%)	0.205	0.351	0.507	0.653	0.775
4 (33.3%)	0.073	0.158	0.276	0.417	0.562
5 (41.7%)	0.019	0.054	0.118	0.213	0.335
6 (50.0%)	0.004	0.014	0.039	0.085	0.158

The probabilities (p-values) for the monitoring of the first 12 subjects were calculated from Binomial distribution.

If there are ≥ 5 subjects with DLTs within the initial 12 subjects at Dose Level 0, up to 24 additional subjects may be enrolled using a design based on Ji et al. [32] (Table 13). If the monitoring guidance indicates escalation (“E”) from Dose Level -1 to Dose Level 0, a maximum of 5 additional subjects will be evaluated at Dose Level 0, up to 17 subjects in all. Therefore, a minimum of 12 subjects (Dose Level 0), and although highly unlikely, a maximum of 41 subjects evaluable for DLT assessment (up to 17 at Dose Level 0 plus 12 each at Dose Levels -1 and -2), may be needed for Dose Evaluation. The pembrolizumab dose will not be changed.

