8.8 Sample Size and Power Calculation

In the Dose Evaluation phase, a minimum of 12 subjects will be evaluated at Dose Level 0.

A potential maximum of 41 subjects may be evaluated across dose levels for DLTs as described in Section 5.2.1.3.4. Twelve subjects evaluated at Dose Level 0 is not entirely based on statistical grounds but would allow for at least 3 evaluated per disease (rrCLL, rrMM, and rrDLBCL) with an overall statistical assessment of the DLT rate as described in [Table 12](#).

In Signal Detection phase, the proposed sample size is 30 subjects for the primary analysis population (ASaT) for each cohort (CLL, MM, DLBCL), 90 in all. With 30 subjects in each cohort, the maximum half-width of the two-sided 95% exact confidence interval for ORR within each cohort is 19%. [Table 20](#) describes examples of 95% confidence intervals per cohort across a possible range of ORRs.

Table 20 Precision (95% Confidence Intervals) for Range of Observed ORR (33% - 83%)

Number of responses/Number of treated subjects (ORR)	95% 2-sided Confidence Interval ^a
10/30 (33%)	(17, 53)
15/30 (50%)	(31, 69)
20/30 (67%)	(47, 83)
25/30 (83%)	(65, 94)

^a exact (Clopper-Pearson) confidence limit for the binomial proportion.
Abbreviation: ORR = objective response rate.

Thus, the minimum and maximum overall sample size for this trial is 102 and 131 subjects, respectively, 12 to 41 subjects from Dose Evaluation plus 90 from Signal Detection. Assuming a 5% non-evaluable rate (ie, not evaluable for DLT in Dose Evaluation or not treated in Signal Detection), a maximum of 138 subjects would be enrolled in this trial.

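### Sections 5.2.1.5 and 8.5 define DLT-evaluable differently, and the 90% dose rule in 5.2.1.5 can replace DLT-free subjects who were dosed exactly as Tables 8 and 9 direct

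*Combined protocol and SAP*

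**What the plan says.** **Planned dosing.** In section 5.2 and Table 3, Cycle 1 dinaciclib is 7 mg/m² on Day 1, with the step-up following: it "will be administered on Day 1, and 10 mg/m² IV on Day 8". From Cycle 2, 14 mg/m² "will be administered on Day 1 and Day 8". Table 11 calls this Level 0. Level -1 is the same in Cycle 1 and 10 mg/m² from Cycle 2.

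**Dose changes for toxicity.** Table 9 covers potassium above the upper limit of normal "occurring during dose-escalation in Cycle 1". The instruction is "Continue with the current dose of dinaciclib and delay dose-escalation until dinaciclib can be administered" without a further rise, and the worked example gives 7, 7, 10 and 14 mg/m². Table 8 requires a one-level reduction when a Day 1 count recovers only outside the 3-day visit window. For Day 8 toxicity, section 5.2.1.3.3 says: "If dose cannot be given within visit window, then Day 8 dose should be skipped".

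**Who is counted.** Section 5.2.1.5 gives as one ground for replacement: "If they receive less than 90% of the total pembrolizumab or dinaciclib in Cycles 1 and 2", provided the subject also had no DLT. Such subjects do not count toward the Dose Evaluation total. 'Total' is not defined, and protocol-directed dose changes are not mentioned. Section 8.5 requires at least one dose and either no discontinuation in the first two cycles or a DLT. It contains no dose percentage.

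**What the count decides.** Section 5.2.1.3.4: "DLTs observed in Cycle 1 and Cycle 2 will be used to evaluate the dose level". Four or fewer DLTs among 12 opens Signal Detection; five or more leads to lower dinaciclib levels. Section 8.1 names DLT as the primary endpoint.

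**The concern.** The 90% threshold does not fit a stepped schedule whose own toxicity rules remove more than 10% of the planned dose. A subject can have a drug-related toxicity, be managed exactly as written, have no DLT, and then be replaced. Section 8.5 would keep the same subject. The denominator of the primary endpoint, and of the 4-versus-5 gate, therefore depends on which section is followed.

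Two things are at stake. First, Table 12 gives the behaviour of the gate for the DLT rate among subjects who are counted. If DLT-free subjects are removed, that is no longer the rate among subjects who were treated. Second, the primary objective is safety and tolerability, and the dose-level DLT count does not show how many subjects could not follow the schedule because of toxicity.

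**Working it through.** **Check on the gate.** With X binomial (n = 12), every Table 12 entry is reproduced as the probability of exceeding the row's count. For example, the row for 4 gives P(X ≥ 5) = 0.158 at a true rate of 0.25 and 0.276 at 0.30, as printed.

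**Dose delivered in Cycles 1 and 2.** Formula: sum of the four dinaciclib doses divided by the planned sum. Level 0 planned sum: 7 + 10 + 14 + 14 = 45; 90% = 40.5. Level -1 planned sum: 7 + 10 + 10 + 10 = 37; 90% = 33.3.

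| Course | Doses (mg/m²) | Delivered / planned | 90% rule, 'total' = planned |
|---|---|---|---|
| Level 0, hyperkalemia after Cycle 1 Day 1 (Table 9 example) | 7, 7, 10, 14 | 38/45 = 84.4% | replaced |
| Level 0, Table 8 delay and reduction at Cycle 2 | 7, 10, 10, 10 (at most) | 37/45 = 82.2% | replaced |
| Level 0, Cycle 1 Day 8 skipped | 7, 0, 14, 14 | 35/45 = 77.8% | replaced |
| Level 0, Cycle 2 Day 8 skipped | 7, 10, 14, 0 | 31/45 = 68.9% | replaced |
| Level 0, hyperkalemia first seen after Cycle 1 Day 8 | 7, 10, 10, 14 | 41/45 = 91.1% | kept |
| Level -1, hyperkalemia after Cycle 1 Day 1 | 7, 7, 10, 10 | 34/37 = 91.9% | kept |

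Under section 8.5 every row is evaluable if the subject does not discontinue within two cycles. If 'total' means the dose prescribed after modification, the Table 9 example is 38/38 = 100% and stays in under both sections.

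**Can these subjects be DLT-free?** Yes. Table 9 acts on any potassium above normal. Section 5.2.1.4 makes a laboratory abnormality a DLT only at Grade 3 or 4 with intervention, hospitalization or persistence beyond a week. A delay to Cycle 2 becomes a DLT under its own criterion only beyond two weeks.

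**Effect on the gate.** The documents give no frequency for such shortfalls, so this is an assumption with a range. Let the true DLT rate among treated subjects be 25%, and let a fraction u of treated subjects be DLT-free and dropped. The rate among counted subjects is 0.25/(1 − u).

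- u = 0: 25.0%, P(X ≥ 5 of 12) = 0.158
- u = 10%: 0.25/0.90 = 27.8%, P = 0.220
- u = 20%: 0.25/0.80 = 31.3%, P = 0.310

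As a second setting, take a true rate of 30% and let q be the share of DLT-free subjects who are dropped. The counted rate is 0.30/[0.30 + 0.70(1 − q)]: 32.3% at q = 10% and 34.9% at q = 20%. P(X ≥ 5) goes from 0.276 to 0.338 and 0.413.

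**The case against.** **Minimum exposure is a legitimate requirement.** A subject who received 69% to 84% of Level 0 says less about Level 0 than one who received all of it. This stands as a design argument, and the fix makes the gate slightly more permissive. It does not explain why section 8.5 omits the requirement, or why the protocol's own toxicity handling should breach it.

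**'Total' may mean the dose prescribed after modification.** Then the conflict in the Table 9 example disappears. The reading is possible, but the rule's only illustration is an infusion stopped for an infusion reaction, a stop that Table 5 itself directs. That points to planned dose. In either case the word needs a definition.

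**Not every such subject is lost.** This is correct: hyperkalemia first seen after Cycle 1 Day 8 passes at 91.1%. However, the scheduled 3- and 5-hour potassium draws in CLL and DLBCL follow the Cycle 1 Day 1 dose, which is the failing case. Some skipped Day 8 doses are logistical, and Table 8 applies whatever the cause, so not every shortfall is drug-related.

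**Stronger readings that the documents do not support.** A reader might infer that the rule hides toxicity by removing these subjects from numerator and denominator alike. It does not: a subject with a DLT is always kept, so only the denominator shrinks. A reader might also count every under-dosed subject as a failure of the dose level, but neither the DLT definition nor the proposed fix does so. Nor do these subjects vanish from the safety record. Section 8.6.5 summarizes adverse events and laboratory tests in Dose Evaluation, and section 5.2.1.3.4 calls the criteria non-binding. Finally, section 8.8 states "Assuming a 5% non-evaluable rate (ie, not evaluable for DLT in Dose Evaluation or not treated in Signal Detection"; without a documented shortfall frequency, that allowance cannot be called wrong.

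**Conclusion.** The inconsistency is real and changes who is counted, so it is more than missing detail. With 'total' read as planned dose, Table 9's own example at Level 0 (84.4%) yields a subject who is replaced under section 5.2.1.5 and evaluable under section 8.5. Table 8 reductions at Cycle 2 and skipped Day 8 doses do the same.

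The bias is upward, toward judging Level 0 too toxic, relative to the DLT rate among all treated subjects. It is modest at a 10% loss (0.158 to 0.220) and material at 20% (0.158 to 0.310), given the assumed 25% rate. The loss fractions are assumptions. The arithmetic on doses and the conflict between the two sections are not. Table 12's probabilities cannot be read as applying to treated subjects until the denominator is settled.

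**What to change.** Reconcile Tables 8 and 9 (section 5.2.1.3.3), section 5.2.1.5 and section 8.5:

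1. Use one definition of DLT-evaluable, worded identically in 5.2.1.5 and 8.5.
2. Measure the 90% against the doses the protocol prescribed for that subject after Tables 8 and 9 and the Day 8 rule. A subject whose dose was held, reduced, skipped or not escalated under those rules because of treatment-related toxicity is then evaluable and not replaced.
3. Keep doses missed for logistical reasons in the denominator, so that those subjects remain replaceable.
4. State whether the infusion-reaction example in 5.2.1.5 is an exception or is withdrawn, so that it does not contradict item 2.
5. Beside the DLT count, report by dose level the number of subjects with a toxicity-driven shortfall in Cycles 1 and 2.

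If Dose Evaluation is already complete, the supplemental analysis plan foreseen in section 8.0 can carry the definition, with the DLT count shown under both definitions.

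The cost is a few sentences and one table row. The downside is that some counted subjects will have had less than full Level 0 exposure and the gate becomes slightly easier to pass; the added row makes that visible. No dosing rule changes.

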5.2.2 Timing of Dose Administration

Pembrolizumab and dinaciclib dosing and schedules are described in Section 5.2.

Trial treatment may be administered up to 3 days before or after the scheduled dosing date for each infusion due to administrative reasons.

Missed doses (ie, Day 8) should be skipped, not delayed, if not given within the allowed window.

Dosing interruptions are permitted in the case of medical/surgical events or logistical reasons (eg, elective surgery, unrelated medical events, radiotherapy, subject vacation, and holidays) not related to trial therapy. Subjects should be placed back on trial therapy within 3 weeks of the scheduled interruption. The reason for interruption should be documented in the subject's trial record. Dosing interruptions should be discussed with the Sponsor.

Details on the preparation and administration of dinaciclib and pembrolizumab are provided in the Pharmacy Manual.

5.2.3 Trial Blinding/Masking

This is an open-label trial; therefore, the Sponsor, investigator and subject will know the treatment administered.

5.3 Randomization or Treatment Allocation

Subjects participating in this trial will be allocated by non-random assignment.

5.4 Stratification

No stratification based on age, sex or other characteristics will be used in this trial.

5.5 Concomitant Medications/Vaccinations (Allowed & Prohibited)

Medications or vaccinations specifically prohibited in the exclusion criteria are not allowed during the ongoing trial. If there is a clinical indication for any medication or vaccination specifically prohibited during the trial, discontinuation from trial therapy or vaccination may be required. The investigator should discuss any questions regarding this with the Sponsor Clinical Director. The final decision on any supportive therapy or vaccination rests with the investigator and/or the subject's primary physician. However, the decision to continue the subject on trial therapy or vaccination schedule requires the mutual agreement of the investigator, the Sponsor and the subject.

All medication taken by the subject within 4 weeks prior to enrollment and all concomitant therapy taken by the subject during the trial up until 30 days after administration of the last dose of trial treatment are to be recorded on the electronic case report form. The identity of the therapy, the dose and the dates started and stopped (or notation of "continuing", as appropriate), and the reason for use must be recorded.

5.5.1 Acceptable Concomitant Medications

Medications required to treat AEs or concurrent illnesses, are allowed during the trial. Antiemetics, including serotonin-receptor antagonists, metoclopramide, prochlorperazine, or thiethylperazine, are allowed throughout the trial.

Contraceptive medications, as per Section 5.7.2, are also allowed. Physiologic replacement doses of glucocorticoids are allowed.

Erythropoietin therapy and granulocyte colony-stimulating factor (G-CSF) are allowed at the discretion of the investigator. Erythropoietin therapy should be used in accordance with the American Society of Clinical Oncology/American Society of Hematology or the National Comprehensive Cancer Network guidelines [33].

G-CSF should be used in accordance with the American Society of Clinical Oncology guidelines [34]. Growth factors are not allowed to be used in order to boost a subject's hematology parameters if the subject is found to be ineligible based on the laboratory results performed at screening.

G-CSF for primary prophylaxis during Cycle 1 in Dose Evaluation is prohibited.

